- 7. Determined the key components of a future cost effectiveness analysis and test data collection methods.
- 8. Established whether pre-set progression criteria are met and a larger scale trial is warranted. If yes, designed the protocol, including identification of required structures, resources and partnerships.

Research design

In line with MRC guidelines on developing and evaluating complex interventions [42], this is a mixed methods, two part feasibility study.

The key research questions include:

For the intervention

- 1. How feasible is it to deliver PuP for opioid-dependent fathers in routine family-based local government and voluntary sector services?
- 2. How acceptable is PuP among staff and recipients and what are the barriers/facilitators to uptake and retention?
- 3. How acceptable and adequate is the training and supervision for staff?
- 4. To what extent can PuP be integrated into non-NHS settings across the UK?

For the study

- 5. What is the optimal level of recruitment, consent, and retention for a future trial?
- 6. What are the best methods of collecting outcome data from fathers and mothers at baseline (pre-intervention), 24 weeks (end of treatment), and at six months follow-up?
- 7. How feasible is it to collect attendance, medical and cost data on participating families?
- 8. How acceptable and appropriate are the assessment methods?
- 9. Is the profile of change in fathers, mothers and children clinically significant?
- 10. What is the nature and extent of routine family support services for fathers in drug treatment?
- 11. Which study design would best suit a future evaluation, including an economic evaluation?

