It should be noted that PuP involves all children living in the family but the focus of this study will be on outcomes for one 'index' child (0-8 years old) in order to maintain a focus on the early years. In order to reduce bias in the selection of the index child, we will use a sampling frame to include different types of children: female/male, age range (lower, middle and upper), children with special needs (e.g. behavioural difficulties, ADHD) and those without. We will then measure this child's progress, using the measures outlined below. In addition, we expect that some families will have other adults (e.g. kinship carers and possibly other fathers) who are involved with the children and who may want to take part in PuP. Where this is appropriate (i.e. in the child's best interests) and relevant to the delivery of the programme (and individualised case plan/case conceptualisation) then wider family members will be encouraged to take part in the programme (i.e. with the agreement of the consenting mother and father and PuP practitioner).

We will recruit families into the study using the following inclusion and exclusion criteria: **Inclusion criteria**:

- 1. Fathers who meet ICD-10 diagnostic criteria for opioid dependence who are prescribed opioid substitution therapy e.g. methadone, buprenorphine.
- 2. Fathers with opioid dependence who also use other types of psychoactive substances (e.g. benzodiazepine, cocaine, cannabis or alcohol) are eligible for inclusion in this study, in recognition that poly-drug use is the norm.
- 3. Mothers/partners of fathers recruited into the study are eligible to take part whether or not they have a diagnosis of substance dependence themselves.
- 4. Each family will have at least one 'index' child aged 0-8 years old, or will be expecting a child.
- 5. Target children included in the study can be biological or non-biological children of the included father.
- 6. Fathers must be involved in the day-to-day care of the index child.
- 7. Fathers must have been in a relationship with the mother/partner for at least 6 months.

Exclusion criteria:

- 1. Either parent has a serious mental illness (e.g. active psychosis) which prevents them from fully participating in the programme.
- 2. Families where domestic abuse or child abuse has resulted in the father being prohibited from contact with the target child or family.

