Assessing recruitment, gathering research data, assessing impact, and a future study: (Research questions 5 – 11 are addressed in this section). Routine data collected by the Research Fellows between May 2017 and October 2018 will provide: detailed quantitative data on participant flow through the study comprising recruitment rates, numbers providing informed consent and numbers completing the outcome measures at baseline, end-or-intervention and at six months follow up. Researcher field notes will provide the reasons for these rates and the best methods of recruiting and retaining participants in the study. We anticipate that we will need to be flexible and dynamic to maximise retention of families, particularly at six months follow-up. All difficulties and solutions (e.g. change of address/mobile phone numbers, use of text messaging and reminders), will be recorded in the final report. At each research interview we will ask families to provide their views on the acceptability and appropriateness of all the measures, including the economic measures, for example, time taken to complete and level of intrusiveness. In addition, we will explore the parent's willingness to provide consent in the future for their routinely collected data to be used in future studies that link data sets to answer questions about long term outcomes.

Although our predominant focus is on questions of feasibility, we will provide an indication of the possible impact of PuP. Analysis of change will include a calculation of the clinical significance of change using the *reliable change index [51]*. The focus will be on measures of parental emotion regulation; emotional availability/antenatal attachment and child abuse potential. Data will be synthesised in the final report and recommendations made as to whether a pilot trial should be conducted and if so, what features should be considered including an economic evaluation. We will use the ADePT process to guide our recommendations [43].

Sample size justification

Our main justification for the sample size of 24 families with a father/male caregiver who is on opioid substitution therapy (OST) is related to the qualitative data collection and analysis requirements, namely:

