- 1. This number is large enough to include a purposive sample of families with differing characteristics to reflect diversity within the larger population of families who would likely take part in a larger trial for example: families with concordant parents (where the mother is also drug-dependent) as well as discordant couples; younger and older fathers; first-time and experienced fathers (with more than one child), resident and non-resident fathers; biological and non-biological fathers. We will develop a sampling matrix to guide recruitment to ensure our study sample reflects the wider population of families seen in routine clinical practice. We will also document a socio-demographic profile of the sample to demonstrate the results of our sampling approach.
- 2. This sample size is also small enough to enable an in-depth analysis of the qualitative data (within the time constraints of the study) to inform our research questions around acceptability, barriers and facilitators to implementation and 'usual care' for fathers. We will conduct in-depth interviews with all parents involved in the study, as well as interviews with the PuP practitioners and focus groups with referring clinicians. We anticipate that this qualitative data will result in lengthy transcripts which will provide rich accounts of involvement in the PuP programme and study. A sample size, limited to a maximum of 24 families, will allow the research team to undertake a more detailed and critical comparative analysis of the whole data set.
- 3. This sample size also allows for an attrition rate of approx. 1/3 of families (n=8) without jeopardising the validity and rigour of the study for example, some may withdraw from the study, or drop out of the intervention or fail to complete follow-up measures. In clinical practice, many of these families stop attending services for a variety of reasons (for example, the children are taken into care, the family moves out of the catchment area, imprisonment, illness/hospitalisation etc) and attendance rates are often poor when compared to other families who have less complex needs. Thus, we calculated a desirable number of families (n=16) to complete the PuP programme and 6 month follow-up measures and then added a hypothetical but realistic attrition rate of 1/3rd to arrive at a sample size of 24 families.

Statistical analysis

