Quantitative data analysis: Descriptive statistics of routinely collected data, including standard deviation values to inform the sample size calculation of the future trial, will provide a profile of the participants and an estimate of study throughput. This will include: number of eligible fathers approached, number who decline to join the study, enrol, complete and drop-out of PuP. Flow of participants through the screening, intervention and follow-up stages of the study will be summarised in a similar manner to the CONSORT guidance for clinical trial reporting.

Quantitative feasibility outcomes (willingness of participants to be randomised; outcome measure completion rates; up-take, retention and follow-up rates) will be summarised by the number and percentage of participants. Descriptive statistics (number and percentage; or mean, standard deviation, median, lower quartile and upper quartile) will be used to summarise pre-treatment, end-of-treatment and follow-up (6 months after treatment completion for: child behaviour (SDQ, BITSEA), paternal and maternal parenting confidence (PSCS), maternal and paternal antenatal attachment (MAAS/PAAS), couple relationship functioning (CTS2), substance use substance related problems (TOP), prescription data, child protection data, sociodemographic data, child and family health, relationship history and paternity. In addition, changes from pre-treatment to each of the subsequent time points will be reported descriptively.

Clinically significant change measure: We will determine the extent to which individual families made clinically significant change using the Reliable Change Index [51]. This will determine whether there has been a reliable improvement in each of the key domains for both fathers/caregivers and mothers on: parental emotion regulation (DERS); emotional availability (EAS); antenatal attachment (MAAS/PAAS); and child abuse potential (B-CAPI). This measure of individual change is able to provide data on the proportion of fathers and mothers who were able to show a clinically significant improvement, those who showed no change and those who deteriorated.

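### Passing the Reliable Change Index is reported as 'clinically significant improvement', so the answer to research question 9 can be overstated

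*Protocol*

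**What the plan says.** Research question 9 (Research design) asks: "Is the profile of change in fathers, mothers and children clinically significant"?

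Two places say how this will be judged.

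- Assessment of efficacy/effectiveness, in the part covering research questions 5 to 11: "Analysis of change will include a calculation of the clinical significance of change using the" reliable change index. The result is offered as an indication of PuP's possible impact.
- Statistical analysis, paragraph on the clinically significant change measure: "We will determine the extent to which individual families made clinically significant change using the Reliable Change Index [51"]. The next sentence describes what the index delivers: "This will determine whether there has been a reliable improvement in each of the key domains for both fathers/caregivers and mothers on" DERS, EAS, MAAS/PAAS and B-CAPI. The paragraph closes by promising "the proportion of fathers and mothers who were able to show a clinically significant improvement, those who showed no change and those who deteriorated".

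The protocol gives no cut-off, normative range, end-state rule or minimal important difference for any of these scales. It also gives no reliability, SD or threshold for the index.

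**The concern.** Within one paragraph the same calculation is first said to show reliable improvement and is then reported as clinically significant improvement. These are different facts. The first says that a change is unlikely to be measurement noise. The second is a claim about how much the change matters or where the parent ends up. The three-class output has no place for a parent whose score moved reliably but who is still in the problem range, so that parent is counted under the stronger label.

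What is at stake is the answer to research question 9 and the impact statement in the final report, which also recommends whether a pilot trial should follow. One of the scales, B-CAPI, measures child abuse potential, which the protocol lists among its primary outcome measures.

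**Working it through.** **The plan's own figure.** The only figure nearby that can be recomputed is the sample size. Sample size justification, item 3, says "we calculated a desirable number of families (n=16) to complete the PuP programme and 6 month follow-up measures" and adds one third for attrition: 16 / (1 − 1/3) = 24 families. This reproduces exactly. The point does not depend on it, but it shows how few parents the proportions will describe.

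**What the index measures.** The protocol gives no formula. In its standard form, with SD the baseline standard deviation and r the reliability:

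RCI = (post − pre) / (SD × √(2(1 − r))), with change called reliable beyond ±1.96.

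The change needed, in SD units, is 1.96 × √(2(1 − r)):

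| r | Change needed (SD) |
|---|---|
| 0.70 | 1.52 |
| 0.80 | 1.24 |
| 0.90 | 0.88 |
| 0.95 | 0.62 |

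The threshold depends only on SD and reliability. A more precise scale lowers the bar, and the final score does not enter. A quantity with these properties measures detectability, not clinical importance.

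**Direction.** Parents who pass the index and also meet an end-state condition are a subset of those who pass the index. The index-only proportion is therefore an upper bound, whatever the inputs. The excess is zero only if every reliable improver also meets the end-state condition.

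**Size, under assumptions.** None of these inputs comes from the protocol. Scores were simulated for 400,000 parents in baseline SD units, with true-score SD √r, error SD √(1 − r) at each time point, individual gain normal with SD 0.5, and the cut-off at 0.

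| r | Baseline mean from cut-off (SD) | Mean gain (SD) | Pass index | Of these, still in problem range | Reliable and crossed |
|---|---|---|---|---|---|
| 0.8 | 1.0 | 0.5 | 18% | 38% | 10% |
| 0.8 | 1.0 | 0.8 | 29% | 33% | 17% |
| 0.7 | 0.5 | 0.8 | 22% | 13% | 15% |
| 0.9 | 1.5 | 0.5 | 29% | 65% | 9% |

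The last two rows are the extremes over r = 0.7 to 0.9, baseline 0.5 to 1.5 SD and gain 0.5 to 0.8 SD.

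For 16 completing fathers in the two central cases:

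- 16 × 0.18 = 2.9 pass, of whom 2.9 × 0.38 = 1.1 are still in the problem range.
- 16 × 0.29 = 4.6 pass, of whom 4.6 × 0.33 = 1.5 are still in the problem range.

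**Second set-up.** Here the cut-off lies midway between a clinical mean and a normative mean 1 to 3 SD apart, with r = 0.8 to 0.9 and mean gain 0.5 to 1.0 SD. The index alone labels 18% to 57% as improved (about 3 to 9 of 16). Requiring reliable change and crossing labels 7% to 30% (about 1 to 5 of 16). The ratio runs from 1.6 to 3.3.

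**The case against.** The strongest reply is that the protocol cites a methodological paper, reference 51, whose title concerns meaningful change and not reliability alone. Naming the index with that citation could be shorthand for a fuller method with its own end-state criterion. Scale-specific cut-offs, SDs and reliabilities are also commonly left to an SAP, which is not at hand. That possibility cannot be excluded. But the protocol itself fixes the index, the label and the three classes. It names no second condition, says the index shows reliable improvement, and leaves no class for reliable change without clinical significance.

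Three stronger readings are tempting, and the document does not support them.

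- *Research question 9 necessarily gets a wrong answer.* Only the direction of possible error is certain. Its size is unknown and could be zero.
- *Parents who start in the functional range will all be reported as unchanged, in the same denominator.* Inclusion criterion 3 might suggest this: "Mothers/partners of fathers recruited into the study are eligible to take part whether or not they have a diagnosis of substance dependence themselves". That criterion concerns diagnosis, not scores on these scales, and Study population describes emotional dysregulation as typical of these parents. No denominator is stated. In the two central cases about 9% to 17% of functional-range starters would still pass the index, and for the others 'no change' is a fair description.
- *Safeguarding is affected.* No safeguarding decision uses this proportion. Protection concerns have their own procedures under Key ethical considerations, and child protection data are collected separately.

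It is also fair that the consequence is limited. The protocol says assessing effectiveness is not a study aim, and nothing in the progression criteria table uses the index.

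**Conclusion.** The point holds as a labelling error in a secondary, descriptive analysis. Followed as written, the protocol reports reliable change as clinically significant improvement. The proportion is an upper bound and can overstate the answer to research question 9 and the indication of PuP's impact.

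The direction needs no assumption about the data. The magnitude rests wholly on assumed reliability, baseline position and gain: about 13% to 65% of those called improved might still be in the problem range. In the central cases that is roughly one to one and a half fathers per scale among 16 completers. The decision on progression is unaffected.

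**What to change.** In both places (Assessment of efficacy/effectiveness and Statistical analysis), report the index result for DERS, EAS, MAAS/PAAS and B-CAPI as reliable improvement, no reliable change or reliable deterioration.

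Use 'clinically significant improvement' only where a cut-off for that scale is stated in advance and the parent both shows reliable change and crosses it. Report that count separately from reliable-only change, with the number of parents who started on the problem side of the cut-off. Where no cut-off is stated, keep to 'reliable change', and say in the answer to research question 9 that clinical significance was not assessed on that scale.

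The cost is a wording change and a little analysis of scores already collected. The headline proportion will usually be lower, and cells will be small with about 16 completing families, so counts should accompany percentages.

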- 1) Document and use mobile phone numbers of both the father, mother and significant others (e.g. siblings and kinship carers) who may know the whereabouts of the family.
- 2) Write to family members with contact verification cards (using reply paid envelopes).
- 3) Use text messaging to send appointment reminders (using study mobile phones).
- 4) Trace the whereabouts of the father/family through professionals involved in the care of the family (e.g. prescribers/GPs, addiction staff, social workers) we will include a parent consent form to enable this kind of contact tracing.

In addition, we will:

- 1) Provide the Research Fellows with a study mobile phone so that participants can telephone or text the researchers direct.
- 2) Send birthday cards to all the family members, Christmas cards and 'father's day'/'mother's day' cards. This strategy has been found to retain families in longitudinal studies.
- 3) Ensure research interviews are arranged at a convenient place and time for participants.
- 4) Repeat offers for follow-up interviews if participants fail to attend research interview appointments.
- 5) Offer each mother and father a gift voucher and expenses for taking part in the research interviews to cover child care costs, travel, subsistence and any other out-of-pocket expenses.
- 6) Escalate payment schedule so that follow-up data is worth more (£15 baseline, £20 end-of-treatment, £25 follow-up).

Outcome measures

As this is a feasibility study, the main study outcome is whether the study meets pre-set progression criteria (see page 4-5). However, the study will also test a range of outcome measures for acceptability and sensitivity to change (see Table below) for use in a subsequent trial.

As the goal of the PuP programme is to improve child outcome and reduce child abuse potential in high risk families, the primary outcome measures will be measures of child outcome, parental report of child abuse potential and safeguarding information on children's involvement in child protection services. Secondary outcome measures will assess the domains of parental functioning that measure the proposed mechanisms of change in the PuP programme that have a direct impact on child outcome. These consist of quality of caregiving relationship, parenting skills and knowledge, and measures that are conceptually related to parental affect regulation including levels of spousal aggression and substance use/misuse.

Table 1.

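### The clinical-change and mean/SD lists do not match research question 9, objective 6 and the named primary measures, and reliable change is labelled clinically significant

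*Protocol*

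**What the plan says.** Research question 9 (Protocol, Research design) reads: "Is the profile of change in fathers, mothers and children clinically significant". Objective 6 (Research objectives) promises outcome measures and a sample size for a possible later trial. The Outcome measures section makes the progression criteria the main study outcome. It then names as primary outcome measures "measures of child outcome, parental report of child abuse potential and safeguarding information on children's involvement in child protection services".

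Under Statistical analysis, the paragraph on clinically significant change applies the RCI, for fathers or caregivers and for mothers, to "parental emotion regulation (DERS); emotional availability (EAS); antenatal attachment (MAAS/PAAS); and child abuse potential (B-CAPI"). The result is reported as "the proportion of fathers and mothers who were able to show a clinically significant improvement", next to those who did not change and those who got worse. The earlier section that says it addresses questions 5 to 11 gives the same scope: "The focus will be on measures of parental emotion regulation; emotional availability/antenatal attachment and child abuse potential".

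The paragraph on quantitative data analysis opens by promising descriptive statistics of routinely collected data, "including standard deviation values to inform the sample size calculation of the future trial". It then lists what is summarised at each visit and as change from pre-treatment: "child behaviour (SDQ, BITSEA), paternal and maternal parenting confidence (PSCS), maternal and paternal antenatal attachment (MAAS/PAAS), couple relationship functioning (CTS2"), followed by TOP, prescription data, child protection data and background data.

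**The concern.** The two lists fix which measure receives which analysis, and three things do not fit the rest of the protocol.

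1. Children are part of question 9, but no child behaviour measure receives the only method offered for judging clinical significance.
2. B-CAPI is one of the primary measures and so a natural candidate endpoint for the next trial. It is not named among the measures given a mean, SD and change; nor are DERS and EAS.
3. A result that shows reliable change is reported under the name of a stronger one.

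If the lists are followed as written, the report has no criterion for importance of change in children. It need not contain the study's own SD for a primary measure. It may also describe as clinically significant a change in a parent whose score is still in the risk range.

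**Working it through.** **Step 1. Set the lists side by side.** Roles come from Outcome measures and Table 1; the last two columns come from Statistical analysis.

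| Measure | Role | RCI list | Mean/SD/change list |
|---|---|---|---|
| SDQ | child behaviour (primary) | no | yes |
| BITSEA | child behaviour (primary) | no | yes |
| B-CAPI | child abuse potential (primary) | yes | not named |
| Child protection records | safeguarding (primary) | no | yes |
| DERS | affect regulation (secondary) | yes | not named |
| EAS | quality of caregiving (secondary) | yes | not named |
| MAAS/PAAS | antenatal attachment (secondary) | yes | yes |
| PSCS, CTS2, TOP | secondary | no | yes |

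Child behaviour scales on the RCI list: 0 of 2. RCI domains not named on the mean/SD list: 3 of 4 (B-CAPI, DERS, EAS). Only MAAS/PAAS is on both lists. It is an antenatal measure, so for a family with no antenatal assessment no RCI measure is on the descriptive list.

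**Step 2. Could EAS stand in for the child?** It is scored from video of parent and child, but Table 1 classes it as quality of caregiving and the RCI paragraph reports it for parents. It is not used here as a child outcome.

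**Step 3. Which children can the child scales cover?** Table 1 gives SDQ for ages 2 to 16 years and BITSEA for 12 to 36 months. The index child may be 0 to 8 years old or not yet born (inclusion criterion 4). A child unborn or under 12 months at baseline has neither scale at baseline, and so no change score. Adding the scales to the RCI list closes the gap for the other children only.

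**Step 4. What does the RCI show?** It divides a person's change in score by the standard error of a difference, which is built from the scale's SD and reliability. A large value means that the change exceeds measurement error. It does not say where the person ends up. The RCI paragraph speaks of reliable improvement and then gives the same result the label clinically significant, with no cut-off or normal-range condition in between.

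**Step 5. Does any planned figure change?** The stated sample size reproduces: 16 / (1 − 1/3) = 24 families. It does not depend on these lists.

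**Step 6. What is an SD from this study worth?** Assume independent, roughly normal scores, one parent per family. The 95% limits for the true SD, as multiples of the observed SD, are √[(n−1)/χ²(0.975, n−1)] and √[(n−1)/χ²(0.025, n−1)].

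- n = 10 (the minimum number of fathers in the progression criteria): 0.69 to 1.83
- n = 16 (target completers): 0.74 to 1.55
- n = 24 (all enrolled): 0.78 to 1.40

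Such an SD is rough, but it would come from the fathers and mothers whom the next trial would enrol.

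**The case against.** Several points on the other side are fair.

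- **The SD promise is general.** The opening sentence on SDs names no scale, Table 1 puts B-CAPI under a child protection heading, and an RCI needs an SD. A reader might infer that no B-CAPI SD can come out of the study. The text does not support that: one could be produced. But the opening sentence concerns routinely collected data, and Table 1 has a separate row for child protection records that fits the listed item more closely. The RCI paragraph calls B-CAPI child abuse potential, and an RCI may be computed with a published SD. Nothing clearly commits the study to report its own.
- **Question 9 is not abandoned for children.** A reader might infer that it cannot be answered at all. SDQ and BITSEA do receive full descriptive statistics and change at each time point, and the section covering questions 5 to 11 says that the analysis of change includes the RCI, not that it stops there. What is missing is a criterion.
- **B-CAPI is not the sole primary measure.** It is one of three kinds, and the main study outcome is the progression criteria.
- **Drop-outs.** Because the RCI paragraph has three result classes and none for parents not assessed, a reader might infer that drop-outs disappear and that improvement is overstated. The protocol does not support this. It schedules the end-of-treatment assessment at completion or at drop-out, and it promises completion and follow-up rates with a CONSORT-style flow. It fixes no denominator for the RCI proportions.
- **Cut-offs.** Their values may be left to the analysis plan. The label, however, is already set in the protocol.

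**Conclusion.** The point stands as a mismatch between explicit lists and the protocol's own question 9, objective 6 and primary measures. Question 9 has no criterion for children (0 of 2 child behaviour scales on the RCI list). Three of the four RCI domains, including a primary measure, are not named among the measures given a mean, SD and change. Reliable change is reported under the name of clinically significant change.

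The consequence is moderate. Effectiveness is not a study aim, no progression criterion uses an RCI or B-CAPI result, and the 24 families stand. The results do feed the recommendation on a pilot trial and the next trial's sample size, so the lists should be reconciled before analysis. The conclusion rests on reading the specific list as fixing what is summarised, and on reading child protection data as the records row of Table 1. On the broadest reading of both, the second gap shrinks to unclear wording, and the first and third remain.

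**What to change.** 1. Add SDQ (age 2 years and over) and BITSEA (12 to 36 months) to the RCI list. State that question 9 cannot be answered with these scales for children unborn or under 12 months at baseline.
2. Name B-CAPI, DERS and EAS in the list of measures given mean, SD and change at each visit, for fathers and mothers separately.
3. Label RCI results *reliable change*. Use *clinically significant* only where the score also crosses a cut-off stated in advance for that scale, if one exists.

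The cost is a few lines of wording and a few table rows, with data already being collected and no change to the sample size. The downsides are that numbers on each child scale will be small, and that fewer parents will be classed as clinically significantly improved.
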